A copy of the consent form will be given to the patient for their review. Consented patients will be given the option of receiving their initial dose of study medication during the same visit, if appropriate, or scheduled at another appointment (7-28 days before their date of surgery) that either coincides with other hospital appointments or necessitates a separate research visit.

X. POTENTIAL RISKS

Risks associated with collection of blood for laboratory tests:

The total amount of blood collected for this study (if the blood tests have not been done as part of the routine care), will not exceed 8mLs per day. The blood sample will be drawn from a venous or arterial catheter, which will be placed in the operating room for routine care. If the IV access from which blood samples can be drawn has already been removed, blood will be drawn from an arm vein.

Risks associated with administration of medications:

Erythropoietin: The safety of using EPO in an acute, perioperative setting has been well established in several meta-analyses.^{1,4-5} The dosing schedule in this study is consistent with phase I and phase II human clinical trials¹⁹⁻²⁰ as well as multicenter clinical trials assessing the optimal and effective dosing of

EPO. The package insert for EPO does not recommend its use in patients undergoing cardiovascular surgery given the lack of sufficient safety and efficacy data; hence its use in this study would be considered “off-label”. As with all erythropoietic therapies, EPO may increase the risk of cardiovascular events, including death. In clinical trials, the most common adverse reactions, encountered in over 5% of EPO-treated perioperative patients, include nausea, vomiting, pruritis, headache, injection site pain, chills, deep vein thrombosis (DVT), cough, and hypertension. Due to the increased thrombotic risk in the perioperative period, DVT prophylaxis is recommended in all surgical patients receiving EPO.²⁹⁻³⁰ Thrombo-prophylaxis in the cardiac surgery consists of sequential compression device, anticoagulation following valve surgery and aspirin following CABG surgery.

Because clinical trials have been conducted under widely varying conditions, adverse reaction rates observed in clinical trials of EPO may not reflect rates observed in our study. The black-box warning issued by the FDA for *chronic* use of erythrocyte stimulating agents in patients with end stage renal disease (ESRD) *and* cardiovascular disease (for increased risk of thrombotic and cardiovascular events) has been challenged by more recent publications outlining differences in the safety profile for short-term use in the perioperative setting. It is important to understand the differences in our patient population when comparing the adverse events listed on the package insert for this drug. First, the majority of adverse events reported by EPO clinical trials have been in chronic renal failure patients and in cancer patients receiving chemotherapy, whom we exclude from our study. Second, our protocol is a short-term (1-4 weeks) in patients experiencing moderate-to-high levels of acute hemorrhage (750mLs-1,500mLs). Third, all of the patients in our study will be anemic; thus the likelihood of having a hematocrit at a level likely to result in a thrombotic complications following CABG surgery is unlikely. Erythrocyte stimulating agents have been used in clinical practice at our institution for over 2 years and increases in the rates of seizure, thrombotic events, pure red blood cell dysplasia, or serious allergic reactions have *not* been observed in patients receiving these medications. The only side effect that has been observed is hypertension. In our study, treatment will be held in patients with blood pressure above 180/100mmHg.

Only one study in the cardiac surgery population has reported an uneven distribution of adverse events and mortality in the EPO-treated versus placebo group (6% vs. 0%, respectively)¹⁵ Although the author of the study concluded there were no differences in adverse events between EPO and placebo-treated patients, an uneven distribution of mortality between the groups cannot be ruled out to any degree of certainty. Remarkably, given the small cohort size of this study, the probability is only 0.229 that, indeed, a statistically significant difference ($p < 0.05$) exists between the EPO versus placebo treated groups.⁴⁸ Of note, an aggressive perioperative dosing regimen was utilized in the protocol of this study and the majority of these patients did *not* have preoperative anemia. In contrast, the remaining clinical trials, conducted over the past decade, have enrolled *anemic* patients and have failed to demonstrate a negative safety signal. More specifically, these trials found no observed difference in mortality, thrombotic

events, or serious adverse events associated with perioperative EPO use.¹⁶⁻¹⁸

This study protocol builds upon the safety profile established with using an *ultra*-short (<5 days) duration regimen recommended in the current practice guideline for cardiac surgery.^{17-18,23,29,30} This study extends the dosing interval to 1-4 weeks in anemic patients using a well-established dosing regimen (300U/kg per dose).²⁹⁻³⁰ Our risk:benefit assessment took into consideration that almost 80% of our patients with preoperative anemia have received erythrocyte transfusions in the past. The use of a novel surveillance strategy in our study provides additional safety measures to further minimize the risk of a thrombotic event.

Feraheme is an iron replacement product indicated for the treatment of iron deficiency anemia in adult patients with chronic kidney disease (CKD). It may cause serious hypersensitivity reactions, including anaphylaxis and/or anaphylactic reactions. In clinical cases,⁴⁶ serious hypersensitivity was reported in 0.2% (3/1,726) subjects. Other adverse reactions potentially associated with hypersensitivity (e.g. pruritus, rash, urticaria, or wheezing) were reported in 3.7% (63/1726) of these subjects. Hypotension may follow feraheme administration. In clinical studies, hypotension was reported in 1.9% (33/1726) subjects, including 3 patients with serious hypotensive reactions. Excessive therapy with parenteral iron can lead to excess storage of iron with the possibility of iatrogenic hemosiderosis (a form of iron overload disorder). Administration of feraheme may transiently affect the diagnostic ability of MR imaging. Alteration of MR imaging studies may persist for up to 3 months following the last feraheme dose. In CKD patients, adverse reactions to feraheme reported in ≤1% of patients are nausea, dizziness, hypotension, peripheral edema, headache, edema, vomiting, abdominal pain, chest pain, cough, pruritus, pyrexia, back pain, muscle spasms, dyspnea, and rash.

There might be other side effects of the study medication that we cannot predict and possibly other side effects that are unknown at this time.

Risk associated with timing of surgery

The protocol is designed to result in no delay from the time when the patient is ready to schedule their surgical date to the day of surgery. The patient and treating physicians may elect to schedule surgery in a manner that would insure the full potential benefits of participation if deemed medically safe.

Risks involved with loss of confidentiality:

Any time information is collected there is a potential risk for loss of confidentiality. Every effort will be made to keep the patient's information confidential; however, this cannot be guaranteed.

XI. SUBJECT SAFETY AND DATA MONITORING

A. Adverse Events (AE):

Adverse events are events that involve physiological, social, or psychological harm to subjects or risks of harm to additional subjects or others. AEs include expected and unexpected harmful effects, and unexpected risks of an interaction or an intervention. AEs may be caused by: the test article or test procedure, other aspects of the interaction or intervention, the subject's underlying condition, or the subject's concurrent standard treatment. AEs may be definitely related, probably related, possibly related, unlikely to be related, or definitely not related *to the research*.

B. Method of Identifying, Recording, Monitoring and Reporting Adverse Events:

We will report all adverse events and other reportable incidences and occurrences to the IRB per reporting guidelines. Any adverse event will be documented of that event including a description, subject number, date, outcome, and follow-up.

C. Safety Endpoints:

The primary safety endpoints of the study are the incidence of adverse events associated with the use of the study medications. These include: hypersensitivity (e.g. pruritis, rash, and urticaria), hypertension, hypotension, bleeding, nausea, vomiting, injection site pain, deep venous thrombosis or other thrombotic complications. Surveillance for these adverse events will be conducted by direct observation (during drug administration), daily bedside visits by the research nurse for the first 7 postoperative days, review of the patient's medical record and listing any of these complication in the Society of Thoracic Surgery (STS) database. The definition of a stroke, myocardial infarction (MI), mesenteric artery occlusion or peripheral vascular event will be based on STS criteria.³⁷ Any event resulting in death from time of initial drug administration to hospital discharge will be recorded.

XII. PROCEDURES TO MAINTAIN CONFIDENTIALITY

We will collect data from lab tests and EPIC, the electronic medical record.

Raw data: We will remove personal identifying information of the patients from the raw data and replace them with coded IDs before data processing and analysis. Any materials containing personal identifying information will be stored in a locked cabinet in the principal investigator's office. After data entry, any materials containing personal identifying information will be promptly and securely returned to the principal investigator. Any materials with personal identifying information on them will be shredded before discard.

Computer files: Computer databases will contain only coded ID information. When computerized names and addresses are needed, they will be kept separate from other project data. All computer files will be password protected. We will destroy any computer disks with personal identifying information before discarding them. Personal identifying information will not be sent via e-mail.

Release of Data sets and Analysis of results: All data and information collected during this study will be considered confidential and remains the sole property of UTSW Medical Center. Data may be shared with AMAG Pharmaceuticals prior to any publications. All data used in the analysis and summary of this study will be anonymous, and without reference to specific subject names. Access to subject files will be limited to the Investigator, authorized clinical research staff and authorized Regulatory Authorities.

The principal investigator must authorize any release of information about the analysis results of the project. However, the UTSW institutional review board or government agencies such as the U.S Food and Drug administration (FDA) may look at and/or copy the patient's medical records for research, quality assurance, and data analysis.

XIII. POTENTIAL BENEFITS

Study participants could potentially increase their red blood cell mass and iron stores before going into surgery. Preoperative anemia is independently associated with a number of postoperative morbidities and mortality. Hence, the treatment has the potential to partially/completely correct preoperative anemia in patients undergoing cardiac surgery and lead to better postoperative outcomes. Anemia is also a major risk factor for allogeneic blood transfusion in the preoperative period. Transfusion has been demonstrated to be significantly associated with increased morbidity. These leading causes of transfusion-related morbidity and mortality are unrelated to viral transmission and include but not limited to changes in the immune system, which cause a stepwise increase in serious complications including postoperative infection, ventilator acquired pneumonia, central line sepsis, acute renal failure, cardiac events, and increased ICU and hospital length of stay. Thus, the treatment has the potential to reduce the transfusion requirement in these patients and improve postoperative outcome and decrease post-operative mortality. The study also has significant potential benefits to society. Transfusion is not only potentially hazardous for the individual patient, but it is also scarce and costly. Blood utilization in America is significantly higher than most Western countries and the gap is increasing. At this same time, the number of eligible donors has been declining because of a growing number of donor deferral criteria instituted to protect the blood supply. This supply and demand mismatch means that blood banks now have to work harder to recruit donors and blood shortages will become more frequent, leading to interruptions in hospital operations and the cancellation of elective surgeries. The total cost of transfusing patients exceeds blood acquisition cost by five times or greater when labor, supplies, blood administration and transfusion-related adverse event costs are considered. Hence, by potentially reducing the transfusion requirement in patients undergoing

cardiac surgery, the study has the potential to improve patient outcome, save lives, conserve a scarce resource, and also decrease the cost for hospitals.

XIII. BIOSTATISTICS

The analysis of this feasibility study will be mainly descriptive and will focus on confidence interval estimation. Results from hypothesis testing will be treated as preliminary and interpreted with caution, as no formal power calculations have been carried out.

Analyses will be performed using parametric and nonparametric univariate and multivariate (where appropriate) statistical methods. Univariate distribution of all variables will initially be performed assessing their distribution with the use of scatter plots and histograms. These results will be used as guidelines in the application of both univariate and multivariate techniques. For descriptive purposes, continuous variables with normal distribution will be described using means, variance and standard deviations; otherwise, medians, interquartile and full ranges will be used. For variables showing distributions that are significantly away from normality, nonparametric statistical tests will be applied. Differences will be considered significant when $P < .05$.

Dichotomous variables will be presented as percentages and analyzed using chi-square or Fisher's exact tests as appropriate. Student t tests or Mann-Whitney U tests will be used to assess differences between independent continuous variables. The analysis of paired continuous variables (such as changes of hemoglobin level or reticulocyte counts from baseline to the day of surgery) will be performed with paired student t tests or Wilcoxon signed rank tests for normally or non-normally distributed variables, respectively. Multivariable regression techniques, including linear mixed models, will be used to analyze differences in continuous variables measured at several different points during the study between the groups (such as hemoglobin level, reticulocyte count, creatinine, etc.) accounting for the within-subject correlation of the data. All statistical analyses will be performed with SAS® software (Version # 9.3, SAS Institute Inc. Cary, NC).

References

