Anemic patients scheduled to undergo CABG, valve, or CABG/valve surgeries will be considered for the study. Patients who fulfill all the inclusion/exclusion criteria will be asked to participate in the study. The proportion of screen failures and eligible patients who refuse to participate will be recorded using a screen failure log. Patients who agree to be in the study and sign an informed consent form will be sequentially enrolled into the treatment group. The treatment group will receive up to three doses of EPO 300U/kg. The first dose of study medication will be administered up to 28 days before the day of surgery and the second will be administered 1-7 days before the day of surgery. These first two doses will be given at least 7 days apart. A third dose may be administered two to four days following surgery. All 3 doses will be administered subcutaneously and per surveillance strategy guidelines. In addition, supplementation

with IV iron (feraheme; 510mg delivered per IV infusion over a minimum of 15 minutes) will be given following the first two preoperative doses of EPO.

Differences in hemoglobin levels and reticulocyte counts from baseline to the day of surgery (preop to POD#0) and postoperative day five (POD#5), proportion of patients receiving erythrocyte transfusions and number of blood products (RBC, platelets and plasma) utilized and pre-defined clinical events (mortality, major cardiac, renal, neurological events [associated with anemia] and infection) will be assessed in all treated participants. Each patient will be enrolled in the study up to 28 days before the day of surgery and for up to 30 days following the day of surgery. This feasibility propensity-matched study will sequentially enroll 23 more treatment subjects to total 25. The propensity-matching control group will be comprised of 25 total “like” patients for comparison. The source of the data for the control group will be the Society of Thoracic Surgery (STS) Database, an institutional registry.

Study medications:

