- Patients in the treatment group will be seen again in a Patient Blood Management infusion room to receive a single subcutaneous injection of EPO 300U/kg and a 2nd IV iron infusion of 510mg, if iron reserves are believed to be inadequate (for a major hemorrhage) based on the result from the baseline iron panel and per Surveillance Strategy guidelines.

- Vitals signs, including heart rate, blood pressure, oxygen saturation, and temperature will be recorded before, during, and after drug administration.
- Patient will be monitored for any serious reactions (anaphylaxis, chest pain, dyspnea, seizures, severe headache, fever, nausea, vomiting, and diarrhea, an increase in blood pressure greater than 20mmHg above baseline systolic, systolic BP greater than 180mmHg and/or diastolic BP greater than 100mmHg, hypotension).
- Approximately 8mLs of blood will be drawn to obtain troponinT/CK-MB and reticulocyte count.
- The visit will last approximately 1 hour.

Day of Surgery

- We will monitor the patient's vitals (blood pressure, EKG, etc) as part of standard care.
- Approximately 8mLs of blood will be drawn to obtain hemoglobin concentration and reticulocyte count.

Post-Operative Dose

- Approximately 3mLs of blood will be drawn for a rotational thromboelastogram (RoTEM) measurement prior to redosing.
- Patients in the treatment group will receive a single subcutaneous injection of EPO 300U/kg two to four days following surgery, if they meet criteria as described in the surveillance plan.
- Vitals signs, including heart rate, blood pressure, oxygen saturation, and temperature will be recorded before and after injection.
- Patient will be monitored for any serious reactions (chest pain, dyspnea, seizures, severe headache, fever, nausea, vomiting, and diarrhea, an increase in blood pressure greater than 20mmHg above baseline systolic, systolic BP greater than 180mmHg and/or diastolic BP greater than 100mmHg).

Post-Operative Days #5, #7, #14

- On Day #5 approximately 8mLs of blood will be drawn to obtain a reticulocyte count, iron panel, AST/ALT.
- On Day #7 approximately 8mLs of blood will be drawn to obtain a reticulocyte count, CBC and creatinine (unless done as SOC).
- On Day #14 or at discharge approximately 6mLs of blood will be drawn to obtain a CBC and creatinine (unless done as SOC).

Clinical Outcomes

The primary objective is to assess the enrollment rate and adherence to the dosing protocol and

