The cost of erythrocyte transfusions, EPO plus iron, direct hospital costs and direct margins associated with the care of those randomized in this pilot study will be recorded for future analysis of resource utilization. The duration of operating room time, intensive care unit and hospital length of stay will be collected. The total cost of erythrocyte transfusion will be based on four times the acquisition cost (\$1,200.00)⁴⁷ The cost of EPO and IV iron will be calculated based on recommended manufacturer suggested retail price at the time of publication and will include activity based costs of administering these treatments based on the protocol outlined in this study.

IV. STUDY PROCEDURES:

Time Line of Pilot Study

Note: Supplementation with intravenous iron (feraheme; 510mg delivered as an IV infusion) will only be administered following the first two preoperative doses of EPO (shown in diagram).

Consort Diagram of Pilot Study:

[figure not shown]

Table 1. SUBJECT SCHEDULE OF EVENTS

Test/evaluation & collected/required forms	7-28d PreOp	1-7d PreOp	POD0 PreOp	POD0 PostOp	POD 1	POD 2	POD 5	POD 7	POD 14
Inclusion & exclusion criteria	X								
Informed consent/HIPAA	X								
Demographics	X								
Medical History/Meds	X								
Physical examination	X	X	X	X	X	X	X	X	X
Body mass index	X								
Vital signs	X	X	X	X	X	X	X	X	X
ASA	X								
Laboratory									
CBC	S	S	S	S	S	S	S	S	S/X
Reticulocyte Count	S	X		X	S		X	X	
Iron panel**	S		X		S		X		
Creatinine	S	S	S	S	S	S	S	S	S/X
Troponin T/CK-MB		X		S	S	S/X			
AST/ALT		S			S		X		
Rotational Thromboelastogram (Rotem) ⁺				S		X			
12-lead EKG	S	S	S	S	S	S	S	S	
Record of Erythrocyte transfusion	X	X	X	X	X	X	X	X	X
Estimated blood loss				X	X	X			
Adverse Events	X	X	X	X	X	X	X	X	X
Patient Survey	X								
Protocol Compliance	X	X	X	X	X	X	X	X	X

S = Standard of Care laboratory tests routinely ordered per ICU care team

X = Not routinely ordered laboratory tests; obtained for research purpose only.

*Will obtain hemoglobin and creatinine on POD14 or before hospital discharge (whichever event occurs first)

**Iron panel includes ferritin, TIBC, iron, transferrin

⁺ Will obtain RoTEM EXTEM 2-4 days after surgery

Adverse events and survival will be reviewed at the time of hospital discharge and 30d following surgery.

V. SUBSTUDY PROCEDURES

Our study does not include any sub-studies.

VI. CRITERIA FOR INCLUSION OF SUBJECTS:

The inclusion criteria of subjects are as follows:

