1. The subject must be between the age of 18 and 80 years old.
2. The subject must be diagnosed with preoperative anemia, defined as hemoglobin <13.0g/dL.
3. The subject must be scheduled for elective cardiac surgery (CABG, valve, or CABG/valve), including both first time and repeat procedures.
4. Female subjects of child bearing potential must have a documented negative pregnancy test within 7 days prior to the procedure.

5. The subject must sign a written informed consent prior to the procedure, using a form that is approved by the UT Southwestern Institutional Review Board.
6. The subject must agree to be compliant and return for all follow-up visits.

VII. CRITERIA FOR EXCLUSION OF SUBJECTS:

The subjects will be excluded if they meet any one of the following criteria:

1. Uncontrolled hypertension (defined as systolic pressure greater than 180mmHg, diastolic pressure greater than 100mmHg, not adequately controlled by anti-hypertensive therapy at the time of procedure).
2. Current renal failure on dialysis or serum creatinine [Cr]>3.0mg/dL. ¹
3. Unstable angina (defined by chest pain and ECG changes indicating ischemia at rest).
4. Thromboembolism within the past year.
5. Current active primary or metastatic malignancy or history of myeloid malignancy.
6. Seizures within the past year.
7. History of stroke within the last 6 months.
8. Patients who have platelet count lower than 50,000/mm³ or coagulation abnormality.
9. Sepsis or bacteremia defined by positive blood culture.
10. Patients who have known hypersensitivity to EPO or any of its components.
11. Patients who have known hypersensitivity to Feraheme or any of its components.
12. Patients who refuse blood transfusion, (i.e. Jehovah's Witnesses).
13. Pregnant or breast feeding.
14. Patients who are unable to provide informed consent or who has inability to understand or cooperate with study procedure.

VIII. SOURCES OF RESEARCH MATERIAL

Data will be obtained from the patient's medical records EPIC and the Society of Thoracic Surgery (STS) database entries. Laboratory tests for reticulocyte count and additional serum ferritin, cardiac biomarkers, serum creatinine, thromboelastographic and liver transaminase measurements will be obtained specifically for research purposes. Other tests conducted (e.g. hemoglobin concentration, creatinine, EKG) will be part of standard of care (see Table 1 for details regarding standard of care and for research only).

IX. RECRUITMENT METHODS AND CONSENTING PROCESS

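### Aims 4 and 5 compare study-monitored treated patients with STS registry controls, so event detection and transfusion oversight may differ between groups in ways matching cannot correct

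*Combined protocol and SAP*

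**What the plan says.** All references are to the combined protocol and SAP.

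- **Groups.** Under Research Design and Methods (section III), consenting patients are "sequentially enrolled into the treatment group". For the 25 controls: "The source of the data for the control group will be the Society of Thoracic Surgery (STS) Database, an institutional registry". The same section says that hemoglobin, transfusion and clinical-event outcomes "will be assessed in all treated participants". No control calendar period is given.
- **Comparison.** Aims 4 and 5 and the secondary outcomes under Clinical Outcomes contrast the two groups on transfusion and on pre-defined events. Most events use STS definitions. Kidney injury uses RIFLE, surgical site infection NHSN, and low-output failure a separately cited definition.
- **Surveillance.** Section XI.C provides bedside research-nurse visits on each of the first 7 postoperative days, record review, and listing of complications in the STS database.
- **Laboratory tests.** Table 1 defines its code: "X = Not routinely ordered laboratory tests; obtained for research purpose only". The pre-op visit has blood "drawn to obtain troponinT/CK-MB and reticulocyte count". Day 7 has "a reticulocyte count, CBC and creatinine (unless done as SOC"), and day 14 or discharge has blood drawn "to obtain a CBC and creatinine (unless done as SOC").
- **Transfusion.** Under Transfusion Strategy, the research nurse records adherence, deviations are discussed with the attending physician, and a justification is requested for units outside the listed criteria. The thresholds are described as current standard of care, and research staff neither order nor prohibit units.
- **Use of the data.** Clinical Outcomes says the data will be used for the power analysis and design of the larger trial. Research Design and Methods says the observed differences are for possible use in its sample size. Section XIII Biostatistics makes the analysis mainly descriptive and treats tests as preliminary.

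**The concern.** A registry control cannot have been visited by the research nurse, had a research-only sample drawn, or had a transfusion discussed as a protocol deviation. An event that only study surveillance finds therefore counts in one group alone. If being observed makes clinicians more sparing with blood, that also happens in one group alone.

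Matching balances baseline covariates that predict treatment. It does nothing about how outcomes are found or how care is supervised after enrollment. The confidence intervals on which the plan relies describe random error, not a one-sided shift. At stake is whether the event and transfusion differences carried into the larger trial's planning reflect the treatment or partly reflect the study procedures.

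**Working it through.** **Step 1: what differs between the groups.**

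- *Nurse visits to day 7.* They presuppose an enrolled patient. They target drug-related events and overlap Aim 5 mainly on thrombosis, bleeding, stroke and myocardial infarction.
- *Troponin/CK-MB.* Table 1 already has it as standard of care after surgery on day 0 and on day 1. The pre-op draw is research-only but precedes surgery, so it cannot detect a postoperative infarction. What remains is day 2 (coded S/X), when not done routinely.
- *Creatinine.* Table 1 codes it S at every visit through day 7 and S/X on day 14 or discharge. What remains is day 14 or discharge, plus any day 7 value not done routinely.
- *Transfusion feedback.* Recording, discussion of deviations and requested justifications all presuppose a patient under the protocol.
- *Definitions.* STS definitions are common to both groups. NHSN infection and low-output failure are not said to be abstracted for controls.

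**Step 2: inputs.** The documents give 25 per group (23 more to total 25, so 2 already enrolled) and a 79% transfusion rate in the center's anemic patients (section II). They give no power figure to reproduce. Every other rate below is assumed. The groups are treated as independent.

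**Step 3: events.** With equal true risk p and relative capture s in controls, the false excess is p − ps. The half-width is 1.96·√[p(1−p)/25 + ps(1−ps)/25].

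- p = 0.10, s = 0.9: excess 0.10 − 0.09 = 0.01, or 0.25 event in 25.
- p = 0.30, s = 0.6: excess 0.30 − 0.18 = 0.12, or 3 events in 25.
- Smallest half-width (p = 0.10, s = 0.6): 1.96·√(0.0036 + 0.002256) = 0.150.
- Largest half-width (p = 0.30, s = 0.9): 1.96·√(0.0084 + 0.007884) = 0.250.

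**Step 4: transfusion.** Take 79% against an assumed 54%. The half-width is 1.96·√(0.79×0.21/25 + 0.54×0.46/25) = 1.96·√(0.006636 + 0.009936) = 0.252. Enumerating all 26×26 pilot results, the Newcombe 95% interval covers the true difference 94.9% of the time with no oversight effect. Coverage is 93.6% if 5 of the 25 points are oversight and 89.2% if 10 are.

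**Step 5: sizing the later trial.** The formula, for two-sided 0.05 and 80% power, is n per arm = [1.96·√(2p̄(1−p̄)) + 0.842·√(p₁(1−p₁) + p₂(1−p₂))]² / (p₁−p₂)². It is assumed that oversight would be shared by both arms of a randomized trial, so it lowers the control rate there.

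- 79% vs 54%: 55 per arm.
- 74% vs 54% (5 points were oversight): 90 per arm; power at 55 is 59%.
- 69% vs 54% (10 points were oversight): 165 per arm; power at 55 is 36%.

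These treat the pilot rates as exact. The next figures allow for pilot sampling error, sizing the trial on the observed rates whenever the pilot favours treatment. They give the chance that true power falls below 50%.

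- Truth 74% vs 54%: 30% with no oversight effect; 33%, 36% and 39% at 1, 2 and 3 points; 45% at 5 points.
- Truth 69% vs 54%: 37% with none; 65% at 10 points.

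**The case against.** The strongest reply is that these are secondary, descriptive outcomes in a 25-versus-25 pilot, already hedged in Biostatistics, and that random error exceeds any plausible shift. That largely stands: every false event excess in step 3 lies inside its half-width, and a 5-point oversight effect costs only about one point of interval coverage. It lowers the severity. It does not remove the point, because the data are meant for trial planning and a one-sided shift adds to random error.

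Several stronger readings are tempting but not supported:

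- *A broad laboratory gap.* Section VIII says that "cardiac biomarkers, serum creatinine, thromboelastographic and liver transaminase measurements will be obtained specifically for research purposes", from which a reader might infer that infarction and kidney injury are measured quite differently. The same section also lists creatinine as standard of care, and Table 1 reduces the gap to the few draws in step 1.
- *Chart labelling as a further difference.* The labelling sentence is conditioned on randomization, which this design does not have. It appears to be left over from a randomized design and cannot be counted as a confirmed difference.
- *A demonstrated oversight effect.* The thresholds are called standard of care and the treating physician decides. Nothing in the documents shows that feedback changes practice. The effect is possible, not established.
- *A trial sized on the pilot difference alone.* The documents speak of use in the power analysis and of possible use in sample size, not of exclusive reliance.

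It is also fair that no sentence says outright that these procedures are confined to treated patients. The follow-up sentence under Clinical Outcomes and the source list in section VIII name no group. The inference rests on consent leading only to treatment and on controls being registry records.

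**Conclusion.** The point holds as a risk of bias. Ascertainment and oversight are, by inference, unequal, and baseline matching cannot repair that. The likely directions are opposite: against treatment for events, in its favour for transfusion. Death and dialysis are less exposed than thrombosis, infarction, kidney injury, infection and low-output failure. The primary feasibility objective is unaffected.

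The size is unknown and may be small beside random error. Only 25 per group and 79% come from the documents; the capture rates, oversight effects and the 54% are illustrations. The sizing figures also depend on which rates are chosen: a 15-point effect needs 165 per arm at 69% vs 54% but 141 at 79% vs 64%. Severity is minor to should-fix.

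**What to change.** 1. For between-group event comparisons, use only events found by routine STS/EPIC abstraction, with the same definitions and window in both groups, plus RIFLE kidney injury from standard-of-care creatinine. Exclude research-only laboratory values and events identified only by study surveillance. Because section XI.C lists these complications in the STS database, STS fields may already hold nurse-found events. Flag the source of each treated-patient STS event so that study-found entries can be removed.
2. Compare NHSN infection and low-output failure only if both groups' charts are reviewed by the same rules. Otherwise report them for the treated group alone.
3. Report surveillance-only events, and events from first dose to surgery, as treated-group safety data.
4. State the control period, and draw controls from operations after the consensus transfusion thresholds were adopted. Reconcile the chart-labelling sentence with the non-randomized design.
5. State that an oversight effect on transfusion is possible and cannot be excluded. If the pilot difference is used for sizing, show sample sizes over the pilot confidence interval and over a range of assumed oversight effects that includes zero.

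The cost is SAP wording, an extraction of routine creatinine, a source flag, and chart review of about 50 patients if item 2's comparison is wanted. The price is fewer comparable events and possibly a smaller control pool. A possible oversight effect remains as a stated limitation.
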